#### 7.4.5 REPORTING OF DEATHS

The investigator must notify the Sponsor as soon as possible, preferably within 24 hours but in no event later than 48 hours, of learning of a participant's death, regardless of whether the death is related or unrelated to the investigational device. The investigator should attempt to determine, as conclusively as possible, whether the death is related to the device. The cause of death and the investigator's discussion regarding whether or not the death was device-related should be described in a written report. The investigator must report death to the reviewing IRB according to the IRB regulations at the study site.

## 8. CLINICAL MONITORING

Clinical site monitoring is conducted to ensure that the rights and well-being of human participants are protected, that the reported trial data are accurate, complete, and verifiable, and that the conduct of the trial is in compliance with the currently approved protocol/amendment(s), with GCP, and with applicable regulatory requirement(s).

- Monitoring for this study will be performed by the Sponsor or Sponsor contract monitor.
- Clinical study site and data monitoring will be conducted via both centralized and on-site monitoring.
  - Centralized data monitoring will focus primarily on:
    - Ongoing, real-time review of clinical data supporting safety, and primary and secondary study-defined endpoints, specifically:
      - Tracking the occurrence of adverse events and expected treatment effects.
    - Ongoing, real-time review of clinical data as entered on Case Report Forms (CRF):
      - Initial study consent was obtained for all enrolled participants;
      - Eligibility for study participation of all enrolled participants;
      - Verification of protocol compliance and data completeness.
    - Ongoing, real-time evaluation of data trends to identify outliers, unexpected trends, or holes in data collection;
    - Ongoing, real-time evaluation of study photographs.
  - Centralized monitoring requires timely data entry and timely uploading of completed CRFs to the study HIPAA compliant cloud-based system (eg ,no later than seven working days after a study visit has occurred).
  - On- site monitoring visits will include:
    - Review of primary/secondary endpoint data source documents;
    - Confirmation that participant randomization is being completed appropriately (if applicable);
    - Confirmation that study blinding is maintained (if applicable);
    - Confirmation of appropriate execution of the PGAIS, SGAIS, PSQ, or other study-specific scales;
    - Note any other study-specific study design items requiring on-site confirmation.
  - General on-site monitoring tasks will include:
    - Review of study conduct and progress at each investigative site (eg, protocol compliance, participant recruitment, etc).
    - Confirmation that written informed consent was obtained and documented at the time

of screening, using an appropriate version of an IRB-approved ICF, and participant eligibility is confirmed.

- Confirmation that all expected treatment effects, adverse events, and/or protocol deviations noted in site records are appropriately documented on study-specific CRFs.
- Identification and resolution of any device performance issues;
- Review of the investigator's study records, study management documents and participant informed consent documents.
- Confirmation that all investigative site personnel with study-related responsibilities are adequately trained and that the applicable training records are maintained in the Site Regulatory Binder.
- Confirmation that study-related responsibilities of site personnel are appropriately documented on the Delegation of Responsibility Log and the log is maintained in the Site Regulatory Binder.
- Reconciliation of the Device Disposition Log against device inventory and confirmation that study devices are kept in a secure location.
- Confirmation that required regulatory documents are present in the Site Regulatory Binder and are current and correct.
- Ensure that all findings, conclusions, and any actions taken to correct deficiencies noted during an on-site monitoring visit are documented in a site monitoring report.

- On-site monitoring frequency
  - An on-site monitoring visit will be completed at each study site at least one time during the course of this clinical trial.
  - The frequency of site monitoring visits may be adjusted based on a number of factors, including but not limited to:
    - Duration of the study;
    - Number of participants enrolled;
    - Number of investigators/sites;
    - Complexity of the study;
    - The level of the study site's experience in conducting and overseeing clinical trials;
    - The quality of the data documented on study-specific data forms and entered into the study database;
    - Number of outstanding issues from previous visits.

## 9. STATISTICAL ANALYSIS

### 9.1 STATISTICAL AND ANALYTICAL PLANS

The primary analysis of efficacy will be by study group and will be based on the evaluable treated participants; hence, only those participants who received complete study treatments and completed a 30-day/90-day follow-up visit post-the-final-treatment-visit, and who have evaluable post-treatment images, will be included in the analysis. Analyses of safety will include all participants who received (complete or incomplete) study treatment.

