#### 2.3.1.1 MINIMIZATION OF POTENTIAL RISKS

The risks listed above are minimized by treating a small area of the skin and noting the participant's sensation and inflammatory response. Potential risks will be further minimized or reduced by monitoring the participant during the treatment/exposure and observing the skin's response to receiving the treatment/exposure. If the treatment/exposure is not tolerated, the investigator (or delegated clinician) must stop administering the exposure for the participant's safety, and the participant will be followed for adverse events for through resolution of the adverse event and/or 30 days.

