## 5.4 PARTICIPANT WITHDRAWAL OR TERMINATION

All participants have the right to withdraw at any point during the study without prejudice. The investigator can discontinue any participant, at any time, if medically necessary. Participants must be discontinued from the investigation by the investigator at any time for any of the following reasons:

- Withdrawal of informed consent.
- Pregnancy (no further study-related treatments will be performed; however, the follow-up visit will be completed if the study treatments has been completed and the participant will be followed to term, called after the pregnancy, child birth, and/or pregnancy termination, and queried for abnormalities or complications).
- Any AEs for which treatment continuation would constitute an unacceptably high-risk for the participant.

The reason for any participant's withdrawal should be documented on the appropriate study-specific data form.

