## 6.3 STUDY TREATMENT

Participants in Group A, the clinical treatment arm, will receive up to 5 treatments at the investigator's discretion using the Mosaic Ultra Treatment Parameter Guidelines as a starting point for the treatment parameters. Treatments will occur 2-6 weeks apart depending on the clinical indication being treated. Participants in Group B, the biopsy arm, will only receive one treatment with pre-determined parameters in a discrete area of the body (such as abdomen, buttocks, back).

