### 9.2 ANALYSIS DATASETS

The following analysis sets will be defined for the statistical analysis of this investigation:

Safety Evaluation Set (SES)

Subset of all participants who received the investigational treatment.

Full Analysis Set (FAS)

Subset of participants in SES that received complete treatments have primary effectiveness data available.

Per Protocol Set (PPS)

Subset of all participants who received complete treatments and have completed the study without major protocol deviations.

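### Sections 9.1 and 9.2 require undefined 'complete' treatment in the primary efficacy set and FAS, so a Group A participant whose course stops early can be left out of the 80% rate even with 90-day images

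*Combined protocol and SAP*

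**What the plan says.** Section 9.1 bases the primary efficacy analysis on "only those participants who received complete study treatments and completed a 30-day/90-day follow-up visit" after the final treatment. Evaluable post-treatment images are a further, separate condition. For safety the rule is wider: "Analyses of safety will include all participants who received (complete or incomplete) study treatment".

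Section 9.2 defines the FAS as "Subset of participants in SES that received complete treatments have primary effectiveness data available" and the PPS as "Subset of all participants who received complete treatments and have completed the study without major protocol deviations".

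Under 6.3, Group A participants "will receive up to 5 treatments at the investigator's discretion", and "Treatments will occur 2-6 weeks apart depending on the clinical indication being treated". The visible text gives no planned or minimum number of sessions. Appendix B (treatment guidelines) is not reproduced and may give one.

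Treatment can stop for safety. Under 2.3.1.1, if exposure is not tolerated, the clinician "must stop administering the exposure for the participant's safety". Section 5.4 lists as a reason for mandatory discontinuation: "Any AEs for which treatment continuation would constitute an unacceptably high-risk for the participant". Section 2.3.1 holds back the next session while severe or prolonged redness lasts.

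The first Group A success criterion in 4.4 is that blinded evaluators pick the post-treatment image correctly in at least 80% of cases.

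**The concern.** Section 9.1 already has an image condition, so missing outcome data are dealt with there. The *complete* condition does something different: it can remove people whose outcome is known. One reason for removal may be a reaction to the device, in which case the reported rate describes those who tolerated the course rather than those who were treated.

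The term is also undefined for a course of discretionary length. The visible text does not say who classifies a course as complete, or when. Membership of the primary set could therefore be settled after the 90-day images have been seen. No planned efficacy set keeps a participant judged incomplete, and no sensitivity analysis is described.

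What is at stake is the reported identification rate and the 80% rule. Safety conclusions are not affected: incomplete treatment stays in the safety analysis, and the adverse event profile is a separate success criterion.

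**Working it through.** The plan gives no expected rate, dropout or derivation for 180, so it has no figure of its own to reproduce. The check compares the texts and then illustrates the size.

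**1. Conditions side by side**

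| Set | Complete treatment | Outcome or follow-up condition |
|---|---|---|
| 9.1 primary | required | 30-day/90-day visit and evaluable images |
| FAS | required | primary effectiveness data |
| PPS | required | study completed, no major deviation |
| Safety | not required | none |

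In the first two rows the conditions are cumulative. Having images does not rescue a participant judged incomplete.

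**2. What *complete* can mean**

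- The whole course. Section 7.4.4 speaks of completing all study treatments, so the protocol does use completion at course level, although in a pregnancy rule. A course cut short is then incomplete.
- Any course ended at the investigator's discretion. Nobody is dropped.
- A session that was not interrupted. An intolerance stop is still dropped; a postponed session is not.

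**3. Which early stops leave 90-day images**

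- *Intolerance (2.3.1.1).* Images can exist: 5.3 asks for follow-up to the end of the study and 6.4 times visits from the final treatment. Section 2.3.1.1 itself mentions follow-up only to resolution and/or 30 days, so how many reach 90 days is unknown.
- *High-risk adverse event (5.4).* The participant leaves the investigation, so images will usually be absent.
- *Redness (2.3.1).* This is a delay. For five sessions, the slack before Day 140 (Table 5) is 140 - 4 x interval, or 84, 56, 28 and 0 days at 2, 3, 4 and 5 weeks. It is often absorbed.

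The route that matters is mainly the first.

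**4. Illustrative size**

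Assumptions, none from the documents except the Group A maximum of 180: all 180 have 90-day images; one reading each; s courses are shortened; the correct-pick rate among them, p, lies between 0.50 (chance between two images) and 1.00.

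Shift from including them, with 80% correct in the others = (s/180) x (p - 0.80):

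- s = 2 (1.1%): -0.3 to +0.2 points
- s = 10 (5.6%): -1.7 to +1.1 points
- s = 18 (10%): -3.0 to +2.0 points

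Let x be the number correct among the other 180 - s. Passing with everyone included needs 0.80 x 180 = 144. The verdict turns from pass to fail if x/(180 - s) >= 0.80 and x + s/2 < 144, and from fail to pass if x/(180 - s) < 0.80 and x + s >= 144.

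| s | Pass to fail | Fail to pass | Rate in the others where the verdict can change |
|---|---|---|---|
| 2 | none | 142 of 178 | 79.8% |
| 10 | 136-138 of 170 | 134-135 of 170 | 78.8% to 81.2% |
| 18 | 130-134 of 162 | 126-129 of 162 | 77.8% to 82.7% |

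Examples for s = 18: 134/162 = 82.7% passes, but (134 + 9)/180 = 79.4% fails; 126/162 = 77.8% fails, but (126 + 18)/180 = 80.0% passes.

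Further from the threshold the verdict is robust. At 90% correct in the others and chance among the shortened, 0.90 x (180 - s) + 0.50 x s < 144 requires s > 45, so 46 of 180 (25.6%).

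**The case against.** The strongest reply is that with no planned number of sessions, any course the investigator ends is naturally complete, so nobody is dropped, and that Appendix B may settle the matter. This reading is available and cannot be excluded. It does not remove the point. Section 9.1 contrasts complete with incomplete treatment, so the plan expects some treatment to be incomplete, and the visible text does not say which.

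A reader might infer that every participant with a reaction is lost from efficacy. The documents do not support that. Withdrawals under 5.4 would usually fail the image condition anyway. Redness only postpones a session, and no rule says treatment becomes incomplete after Day 140. Five sessions at the permitted 6 weeks reach Day 168 (4 x 42) without any reaction, which is a scheduling inconsistency and a separate matter. An intolerance stop does not by itself bar later sessions, and 6.3.2 allows settings to be adjusted after test spots.

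A reader might also infer that the rule inflates the success rate. The direction is not known. Evaluators pick the later image; they do not grade improvement. Lasting redness, discoloration or scarring could make that image easier to pick, so leaving these participants out could lower the rate.

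Finally, this is a non-randomized pilot with descriptive summaries, and a completer analysis is legitimate when declared. That stands for the PPS, where requiring complete treatment is ordinary. It does not explain why the FAS carries the same restriction, and 4.4 still applies a pass/fail rule to the rate.

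**Conclusion.** The concern holds in limited form. As written, the primary set and the FAS can leave out treated Group A participants who have 90-day images, on an undefined criterion that could be applied after the images are seen. Intolerance stops are the main route.

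The number affected and the direction of the shift cannot be obtained from the documents. On the assumptions above, the rate moves by a fraction of a point with 2 shortened courses and by at most 3.0 points with 18, and the 80% verdict changes only when the rate in the others is close to 80%. There is no effect if no course is shortened, or if every course ended at discretion counts as complete. The point does not concern a hypothesis test, the safety analysis or the PPS restriction as such. It merits an amendment because the wording is cheap to correct.

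**What to change.** For Group A:

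1. In 9.1 and in the FAS, replace the complete-treatment condition with: at least one treatment session and evaluable baseline and 90-day images, whatever the number of sessions.
2. Keep *complete* for the PPS only, defined as a course that reached five sessions, or that the investigator ended for a reason other than intolerance, an adverse event or withdrawal.
3. Report the identification rate in both sets.
4. Report the number of courses shortened for safety reasons, and how many of those have 90-day images.

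The cost is amendment wording in 9.1 and 9.2 and one CRF item giving the reason the course ended. No visits are added, because follow-up is already timed from the final treatment.

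The downside is that the primary rate then mixes full and partial courses and may move slightly in either direction; the PPS still gives the finished-course rate. The change does not recover treated participants without 90-day images, so some selection on tolerability can remain. Item 4 makes its extent visible.

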### 9.2 ANALYSIS DATASETS

The following analysis sets will be defined for the statistical analysis of this investigation:

Safety Evaluation Set (SES)

Subset of all participants who received the investigational treatment.

Full Analysis Set (FAS)

Subset of participants in SES that received complete treatments have primary effectiveness data available.

Per Protocol Set (PPS)

Subset of all participants who received complete treatments and have completed the study without major protocol deviations.

## 9.3 DATA SUMMARY

At the conclusion of the study the data will be analyzed and summarized in a report. Categorical values (such as sex, ethnicity, satisfaction results, etc.) will have both their number of occurrences as well as the frequency of those occurrences reported. For continuous variables (such as age, treatment pain scores, etc.) the minimum, maximum, average, median, and standard deviation will all be reported.

## 10. SOURCE DOCUMENTS AND ACCESS TO SOURCE DATA / DOCUMENTS

Source documents are defined as the results of original observations and activities of a clinical investigation. Source documents will include, but are not limited to, study-specific data forms, progress notes, electronic data, computer printouts, screening logs, and recorded data from automated instruments. All source documents pertaining to this study will be maintained by the investigators and made available for inspection by authorized persons.

Following written SOPs, the clinical study monitors will verify that the clinical trial is conducted, and data are generated, documented (recorded), and reported in compliance with the protocol, GCP, and the applicable regulatory requirements.

The investigational site will provide direct access to all trial related sites, source data/documents, and reports for the purpose of monitoring and auditing by the sponsor, and inspection by local and regulatory authorities.

## 11. ETHICS/PROTECTION OF HUMAN PARTICIPANTS

### 11.1 ETHICAL STANDARD

This clinical study will be conducted in accordance with the Protection of Human Subjects Regulations, including Subpart B Informed Consent of Human Subjects (21 CFR Part 50); the Institutional Review Board Regulations (21 CFR Part 56); the Financial Disclosure by Clinical Investigators Regulations (21 CFR Part 54); and the Investigational Device Exemptions Regulations (21 CFR Part 812), and the ICH E6.

### 11.2 INSTITUTIONAL REVIEW BOARD

Prior to initiation of any study procedures, the protocol, informed consent, and recruitment materials, and all participant materials will be submitted to a duly constituted IRB for review and approval. In addition, any amendments

to the protocol or Informed Consent Form will be reviewed and approved by the IRB. The Sponsor must receive a letter documenting IRB approval at the clinical site prior to the initiation of the study.

The investigator is responsible for providing the appropriate reports to its reviewing IRB during the course of the clinical study. These reports will include:

1. Informing the IRB of the study progress periodically as required, but at least annually;
2. Reporting any unanticipated adverse device effects within 10 working days of first learning of the event;
3. Reporting any deviations from the clinical protocol to protect the life or well-being of a participant, in the case of an emergency, within five working days after the emergency occurred;
4. Reporting the use of the device without obtaining informed consent from a participant within five working days of the event; and
5. Providing any other reports requested by the IRB.

The IRB must be notified of study completion within 30 days of the final visit of the last participant and should be provided with a summary of the results of the study by the investigator.

## **11.3 INFORMED CONSENT PROCESS**

### **11.3.1 CONSENT/ASSENT AND OTHER INFORMATIONAL DOCUMENTS PROVIDED TO PARTICIPANTS**

Consent forms describing in detail the study device, study procedures, and risks are given to the participant and written documentation of informed consent is required prior to starting intervention/administering study product.

### **11.3.2 CONSENT PROCEDURES AND DOCUMENTATION**

Informed consent will be obtained from all participants prior to study participation. Informed consent is a process that is initiated prior to the individual's agreeing to participate in the study and continues throughout the individual's study participation. Extensive discussion of risks and possible benefits of participation will be provided to each participant. Consent forms will be IRB-approved, and the participant will be asked to read and review the document. The investigator, or investigator-delegated study personnel, will explain the research study to the participant and answer any questions that may arise. All participants will receive a verbal explanation in terms suited to their comprehension of the purposes, procedures, and potential risks of the study and of their rights as research participants. Participants will have the opportunity to carefully review the written consent form and ask questions prior to signing. The participants should have the opportunity to discuss the study with their surrogates or think about it prior to agreeing to participate. The participant will sign the informed consent document prior to any procedures being done specifically for the study. The participants may withdraw consent at any time throughout the course of the trial. A copy of the informed consent document will be given to the participants for their records. The rights and welfare of the participants will be protected by emphasizing to them that the quality of their medical care will not be adversely affected if they decline to participate in this study.

## **11.4 PARTICIPANT AND DATA CONFIDENTIALITY**

All information generated in this study must be considered highly confidential and must not be disclosed to any persons not directly concerned with the study without prior written permission from the Sponsor. Authorized regulatory officials and Sponsor personnel (or its representatives) will be allowed full access to inspect the records. All investigational devices and/or other materials collected will be used solely in accordance with this protocol, unless otherwise agreed to in writing by the Sponsor.

Participants should be identified only by initials and unique participant numbers on study-specific data forms. If necessary, their full names may be made known to a regulatory agency or other authorized officials.

